#### 9.1.5.1. Grade 1 or 2 Local or Systemic Reactions

Local reactions of mild (Grade 1) or moderate (Grade 2) severity will usually resolve spontaneously. If needed, they may be managed with a combination of medical treatment measures as appropriate.

### 9.2. Toxicity Management

#### 9.2.1. Adverse Events

Reports of AEs will be elicited by verbally questioning the participant at all visits. The study coordinator will also telephone the participant approximately 2 to 3 days after the HXTC study product administration to inquire about any potential treatment emergent adverse events (TEAE). The participant will be instructed to contact the study coordinator or investigator if such events occur at any point during the study.

Any events spontaneously reported by the participant or observed by the study team will be recorded.

If an AE occurs, the study coordinator, in collaboration with the PI or designee, will evaluate the severity and seriousness of the AE and the relationship to the study product, and will document the findings. Appropriate countermeasures, including medical intervention or procedures, must be instituted if indicated clinically.

AEs occurring at the HXTC administration site should be reported and analyzed in accordance with standard practices for clinical testing of novel therapeutic candidates.

All reactions will be graded according to the Division of AIDS (DAIDS) Table for Grading the Severity of Adult and Pediatric Adverse Events, Version 2.1 [July 2017], which is available on the DAIDS RSC website: <http://rsc.techres.com/safetyandpharmacovigilance/>.

#### 9.2.2. Definition of an Adverse Event (AE)

An AE is any untoward medical occurrence in a participant administered a pharmaceutical product that does not necessarily have a causal relationship with the treatment.

An AE can therefore be any unfavorable or unintended sign (including an abnormal lab finding, for example), symptom, or disease temporally associated with the use of a study drug, whether or not considered related to the study drug.

An AE does include a/an:

- Exacerbation of a pre-existing illness
- Increase in frequency or intensity of a pre-existing episodic event or condition
- Condition detected or diagnosed after study product administration even though it may have been present prior to the start of the study
- Continuous persistent diseases or symptoms present at Baseline that worsen following the start of the study

An AE does not include a/an:

- Medical or surgical procedure (e.g., surgery, endoscopy, tooth extraction, transfusion); however, the condition that led to the procedure is an AE
- Pre-existing diseases or conditions present or detected at the start of the study that do not worsen
- Situations where an untoward medical occurrence has not occurred (e.g., hospitalizations for cosmetic elective surgery, social, or convenience admissions)
- The disease or disorder being studied or sign or symptom associated with the disease or disorder unless more severe than expected for the participant's condition
- Overdose of either the study medication or concurrent medications without any signs or symptoms

In general, abnormal laboratory findings (e.g., clinical chemistries, hematology, urinalysis) or abnormal assessments (e.g., vital signs) are not recorded as AEs unless they are considered clinically significant by the investigator. If an abnormal lab finding is considered clinically significant, it must be recorded in the AE log as follows:

- If it contributes to a clinical diagnosis, the diagnosis must be recorded as the AE (e.g., a clinically significant elevation in blood glucose must be recorded as "diabetes" if a clinical diagnosis is made)
- Or if an abnormal finding does not indicate a clinical diagnosis, the abnormality itself must be recorded

#### 9.2.3. Adverse Event Reporting Period

The AE reporting period for each participant begins when the participant signs the consent and lasts through the 30 days following the EOS visit in Step 6, Visit 24. During Step 1 and Step 3 (prior to study product administration), any AE that occurs will be collected as concurrent medical history (pre-existing condition) and not as an AE, unless it is due to a protocol-related procedure (e.g., leukapheresis or large blood collection for HXTC manufacturing).

AEs leading to discontinuation, AEs of  $\geq$  Grade 3 severity, related adverse events, and lab abnormalities as well as safety concerns will be recorded in the database as well as communicated in a timely manner to the UNC IRB, Children's National Health System IRB, NHLBI, FDA, and Merck per the reporting requirements of each regulatory entity.

The Sponsor of this study is UNC-CH. The principal investigator ([name]) at UNC-CH will be responsible for reporting to all the regulatory bodies and funding sources listed above.

#### **9.2.4. Documentation of Adverse Events**

Throughout the trial, the study coordinator will monitor closely for the development of AEs and the investigator or designee will determine clinical significance of AEs, and initiation of medical interventions if required.

Record the following in the participants' study chart:

- Concise diagnosis
- Onset date
- Criteria for regarding as an AE
- Setting
- Resolution date
- Severity (per DAIDS toxicity grading table)
- Relation to the study product (unrelated, unlikely, possibly, probably, definitely); an AE may be considered related if it follows a reasonable temporal sequence from administration of the study product, confirmed by improvement when the product is stopped and re-appears on repeated exposure
- Study product change (interrupted or discontinued)
- Seriousness (not serious, fatal, life-threatening, leads to or prolongs hospitalization, results in persistent or significant disability or incapacity, congenital anomaly or birth defect, important medical event)

#### **9.2.5. Definition of a Serious Adverse Event**

As provided in Title 21 CFR part 312, an SAE is an AE occurring at any dose that results in any of the following outcomes:

- Death
- A life-threatening AE
- Inpatient hospitalization or prolongation of existing hospitalization
- A persistent or significant disability or incapacity
- A congenital anomaly or birth defect
- Important medical event that may not result in death, be life-threatening, or require hospitalization may be considered serious when, based upon appropriate medical judgment, it may jeopardize the participant and may require medical and surgical intervention to prevent one of the outcomes

Any death (regardless of cause) that occurs from the time of the study product administration until 32 weeks after the final study product administration, and any death occurring after this time that is judged at least possibly related to prior treatment with the study product, will be promptly reported.

#### **9.2.6. Definition of a Serious Unexpected Adverse Event**

A serious adverse drug reaction is defined as an SAE that is not identified in the IB(s).

#### **9.2.7. Reporting of Serious Adverse Events**

All SAEs occurring during the study will be reported to the UNC IRB per the UNC IRB reporting requirements, NHLBI, the FDA, CNH IRB, and Merck, if required within 24 hours of knowledge of the occurrence. A written report (UNC IRB Unanticipated Problem Report Form and, if required Med Watch Form FDA 3500) will be faxed or sent within 24 hours of knowledge of the occurrence. Additional information will be supplied as requested. The funding source of this study is the NHLBI. The principal investigator ([name]) at UNC-CH will be responsible for reporting to all of the regulatory and funding agencies.

#### **9.2.8. Follow-Up of AEs and SAEs**

All AEs and SAEs must be followed until resolution, become chronic, or stable. The resolution status of such an event must be documented. In addition, the principal investigator should report all follow-up for reportable SAEs to the UNC and CNH IRBs, NHLBI, FDA, and Merck.

#### **9.2.9. Post-Study AEs and SAEs**

Investigators are not obligated to actively seek AEs and SAEs in former study participants. However, if the PI learns of an SAE during the 30 days following the final study visit, the PI must promptly notify the NHLBI.

### **9.3. Discontinuation of HXTc and/or VOR**

Participants who prematurely discontinue the HXTc infusions or VOR should continue to undergo the protocol evaluations as per the Schedule of Events.

The End of Study Intervention visit (Study Visit 23) will be also conducted any time a participant discontinues early from the study after receiving combination therapy with VOR and HXTCs in Steps 4 and 5 or upon the successful completion of the study interventions. If HXTc or VOR has been administered, the investigator must make every effort to perform the evaluations four weeks after the participant's last dose but not more than 8 weeks in cases where the participant does not agree to conduct the remaining scheduled visits. Participants terminating early from the study after receiving combination therapy will be asked to complete the follow-up visit (Study Visit 24) after Visit 23 in Step 6.

### **9.4. Pregnancy**

If the pregnancy test is positive at screening, the potential participant will not be allowed to enroll on the study. No further evaluations are necessary.

If the participant becomes pregnant during the study, then study treatment must be discontinued immediately. The participant may continue in the study in an off treatment/on study status for safety labs only. The participant will be followed until the pregnancy outcome and up to 8 weeks after the delivery.

All participants who become pregnant must be followed to the completion/termination of the pregnancy. If the pregnancy continues to term, the outcome (health of infant) must also be reported to the UNC and CNH IRBs if required per their reporting requirements, the NHLBI, the FDA (US Food and Drug Administration), and Merck Research Laboratories.

If a partner to a male study participant becomes pregnant, while male participant is actively on study, the pregnancy must be reported. The study investigator will make every effort to obtain permission to follow the outcome of the pregnancy and report the condition of the fetus or newborn to the UNC and CNH IRBs if required per their reporting requirements, NHLBI, FDA, and Merck without delay and within 24 hours if the outcome is an SAE (e.g., death, abortion, congenital anomaly, or other disabling or life-threatening complication to the mother or newborn).

Although not considered an adverse experience, it is the responsibility of investigators or their designees to report any pregnancy in a participant or participant's partner (spontaneously reported to them) that occurs during the study or within 12 weeks of completing the study.

We will obtain a medical release or separate consent granting permission to follow the health of both the pregnant participant and her unborn child. We will conduct a post-delivery interview and complete a case report form (CRF) to collect the data related to the pregnancy outcome.

The Sponsor of this study is the University of North Carolina at Chapel Hill. The principal investigator ([name]) at UNC-CH will be responsible for reporting to all regulatory agencies and funding sources listed above.

## **10. STATISTICAL CONSIDERATIONS**

### **10.1. General Design**

This is a phase I, single-site study to evaluate the effects of VOR and HXTC therapy on persistent HIV-1 Infection in HIV-infected individuals suppressed on ART. Twelve participants with durable viral suppression will be enrolled and will complete the study. All participants will receive the same treatment and if eligible, will be dosed with VOR and receive HXTC infusions. Participants will continue their baseline ART regimen throughout the study.

If the baseline IUPM  $\geq 0.3$ , participants will have a blood sample sent to CNH for production of HXTCs. Upon release of HXTC, participants will be clinically assessed to complete the two treatment series with oral VOR 400 mg doses combined with HXTC infusions over a 3 month period. VOR will be administered every 72 hours and each treatment series will consist of 10 doses of VOR 400 mg.

In Step 4 (Series 1), participants will receive two HXTC infusions along with 10 doses of VOR 400 mg. The HXTC infusions will be administered 6 hours after the 1st and 6th VOR doses.

In Step 5 (Series 2), participants will receive three infusions along with 10 doses of VOR 400 mg. The first two infusions will be administered 6 hours after the 11th and 16th doses of VOR. The 5th and final HXTC infusion will occur 1 – 3 days after the 20th VOR dose.

The 2nd and final leukapheresis will occur at least 4 weeks after the last HXTC infusion.

Resting cell infection frequency will be determined pre VOR-HXTC dosing with the baseline leukapheresis and post VOR-HXTC dosing with 2nd leukapheresis.

Longitudinal follow-up to measure the effectiveness of the intervention will continue for 9 weeks after the last HXTc infusion. Serial blood draws will be obtained pre and post-VOR-HXTc dosing throughout the study to monitor immune response.

#### **10.1.1. Study Hypothesis**

We hypothesize that HXTCs can be safely combined with VOR, and allow depletion of persistent HIV infection.

### **10.2. Outcome Measures**

#### **10.2.1. Primary Endpoints**

##### **10.2.1.1. Safety**

Occurrence of at least one  $\geq$  Grade 3 adverse event including signs/symptoms, lab toxicities, and/or clinical events that is possibly or definitely related to VOR or HXTc any time from the first day of study treatment through Step 6, Visit 23.

Safety data will include local and systemic signs and symptoms, laboratory measures of safety/toxicity, and all adverse and serious adverse events. Safety data will be routinely collected throughout the duration of the study.

NOTE: The occurrence of a Grade 3 infusion reaction that is sustained for less than 48 hours will not be included as a primary safety endpoint.

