### **9. CLINICAL MANAGEMENT ISSUES**

Criteria for participant management, treatment interruption, and study discontinuation will be mandated only for toxicities possibly, probably, or definitely related to HXTC and/or VOR.

NOTE: In the event that a participant develops toxicity related to his/her previously-stable ART, consultation with the protocol team will be required (preferably before appropriate therapy modification). Toxicities due to drugs in the antiretroviral regimen should be managed according to standard clinical practice, with the goal of maintaining continuous therapy, if possible.

AEs assessed as related to non-study drugs (concomitant medications) should be handled according to the relevant package inserts and the best medical judgment of the site investigator or designee.

Infusion site reactions will be graded according to the DAIDS toxicity grading table.

U.S. Department of Health and Human Services, National Institutes of Health, National Institute of Allergy and Infectious Diseases, Division of AIDS. Division of AIDS (DAIDS) Table for Grading the Severity of Adult and Pediatric Adverse Events, Version 2.1. [July 2017], which is available on the DAIDS RSC website.

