### **9.1.1. Grade 1 or 2 Toxicity**

Participants who develop a Grade 1 or 2 AE or toxicity that occurs following an HXTC infusion or VOR dosing that is thought to be possibly, probably, or definitely related to HXTC and/or VOR should be discussed with the study team.

In the event of a grade 1 toxicity related to hemoglobin or anemia the study team should be contacted to guide the elimination of research labs as needed to avoid a grade 2 toxicity related to hemoglobin.

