### **9.1.2. Grade 3 Toxicity**

For participants who develop a Grade 3 AE that occurs following an HXTC infusion or VOR dosing not specifically discussed below that is judged by a site investigator to be at least possibly study treatment-related, the protocol team must be notified within 24 hours. Participants with a study treatment-related Grade 3 AE will not receive any additional doses of study treatment/product. Participants experiencing Grade 3 AEs should be followed closely and if the AE does not return to Grade  $\leq$  2 within 2 weeks, the protocol team should again be notified within 24 hours.

For participants who experience a Grade 3 AE that is judged not related to the study drug by the investigator or designee, continued study participation is at the discretion of the principal investigator in consultation with the protocol team.

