### **9.1.3. Grade 4 Toxicity**

For participants who develop a Grade 4 AE that occurs following an HXTc infusion or VOR dosing not specifically discussed below that is judged by a site investigator or designee to be at least possibly study treatment-related, the protocol team must be notified within 24 hours. Participants with a study treatment-related Grade 4 AE will not receive any additional doses of study treatment/product. Participants experiencing Grade 4 AEs should be followed closely with additional clinical assessments and laboratory testing as clinically indicated. If the AE does not return to Grade ≤ 2 within 2 weeks, the protocol team should again be notified within 24 hours.

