#### **9.1.5. Systemic Reactions**

The protocol team should be contacted within 24 hours for any non-local Grade 3 or 4 AE thought definitely, possibly, or probably related to study treatment. Additional study product should not be administered prior to consultation with the

protocol team. For severe infusion (Grade 3 or 4) reactions, appropriate medical therapy including epinephrine, corticosteroids, intravenous antihistamines, and oxygen should be available for use in the treatment of such reactions. Participants should be carefully observed until the complete resolution of all signs and symptoms. In each case of an infusion reaction, the site investigator should institute treatment measures according to the best available medical practice.

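### The primary safety endpoint leaves out events rated *probably* related, a level that the causality scale and the suspension rule both include

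*Combined protocol and SAP*

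**What the plan says.** Section 10.2.1.1 makes the primary safety endpoint the occurrence, per participant, of at least one Grade 3 or higher adverse event "that is possibly or definitely related to VOR or" HXTC, from the first day of study treatment through Visit 23. A NOTE in the same section takes Grade 3 infusion reactions lasting under 48 hours out of the endpoint.

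Section 9.2.4 sets the scale on which causality is recorded: "Relation to the study product (unrelated, unlikely, possibly, probably, definitely". It has five levels, three of them positive.

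Other sections that depend on causality take in all three positive levels:

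- Section 9, on participant management: "mandated only for toxicities possibly, probably, or definitely related to HXTC and/or VOR".
- Section 9.1.1, Grade 1 or 2: "thought to be possibly, probably, or definitely related to HXTC and/or VOR".
- Section 9.1.2, Grade 3: "judged by a site investigator to be at least possibly study treatment-related".
- Section 9.1.3, Grade 4: "judged by a site investigator or designee to be at least possibly study treatment-related".
- Section 9.1.5, non-local Grade 3 or 4 events: "thought definitely, possibly, or probably related to study treatment".
- Section 10.5: enrollment is suspended once two or more participants have a Grade 3 or higher toxicity at any of the three positive levels, as judged by the protocol team.

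Section 10.4 speaks only of treatment-related toxicity and lists no levels. Section 10.3 states its precision intervals for primary adverse events, which are the events that 10.2.1.1 defines.

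**The concern.** The endpoint names the weakest and the strongest positive attribution and skips the one between. Nothing in the documents explains why an event judged *possibly* related should count when one judged *probably* related does not.

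Safety is the first primary endpoint in 10.2.1 and the primary outcome in 3.2.1. An analyst who codes the event from 10.2.1.1 has a two-level list to follow; one who works from 10.5 would code three levels. The same data could then give two different primary safety rates, and an event could count toward suspending enrollment without counting toward the primary rate. The literal reading can only lower the reported rate. With 12 participants, a single event visibly changes the result.

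**Working it through.** **1. Comparison of the text.** Positive levels counted in each place:

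| Section | *possibly* | *probably* | *definitely* |
|---|---|---|---|
| 9.2.4 (recorded scale) | yes | yes | yes |
| 9, 9.1.1, 9.1.5 | yes | yes | yes |
| 9.1.2, 9.1.3 (threshold wording) | yes | yes | yes |
| 10.5 (suspension rule) | yes | yes | yes |
| 10.2.1.1 (primary endpoint) | yes | **no** | yes |

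No section says that the two-level wording stands for a range or that *probably* is folded into another level. The one deliberate exclusion in 10.2.1.1 is spelled out in its NOTE, and there is no such note for *probably*.

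**2. The plan's own figures.** Inputs: n = 12, with two-sided exact 95% limits (10.3) and one-sided exact 95% and 80% limits (10.4). The Clopper-Pearson limits for x events in n at two-sided level α are

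- lower = Beta quantile(α/2; x, n − x + 1), or 0 if x = 0;
- upper = Beta quantile(1 − α/2; x + 1, n − x).

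One-sided upper limits use 1 − α in place of 1 − α/2.

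| Result | Two-sided 95% | Plan (10.3) | One-sided 95% / 80% upper | Plan (10.4) |
|---|---|---|---|---|
| 0/12 | 0 to 0.2646 | [0.00, 0.26] | 22.1% / 12.6% | 22% / 13% |
| 1/12 | 0.0021 to 0.3848 | [0.00, 0.38] | 33.9% / 23.0% | 34% / 23% |

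All the printed figures are reproduced. Adding *probably* changes none of them, because it alters which events are counted and not n or the method.

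**3. Effect on a reported result.** This is an illustration, not a forecast. Suppose one participant's only qualifying event is rated *probably*.

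- Denominator 12. Literal reading: 0/12, upper limit 1 − 0.025^(1/12) = 0.2646, so 0 to 26%. With *probably* counted: 1/12 = 8.3%, interval 0.2 to 38%.
- Denominator 13. Section 9.1.2 says "Participants with a study treatment-related Grade 3 AE will not receive any additional doses of study treatment/product", and 10.4 replaces anyone who does not receive the full treatment. If all treated participants stay in the denominator, the literal reading gives 0/13, upper limit 1 − 0.025^(1/13) = 0.2471, so 0 to 25%. With *probably* counted: 1/13 = 7.7%, interval 0.0019 to 0.3603, so 0.2 to 36%.

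If two of 12 participants had only such events, the literal result would still be 0/12 (0 to 26%) instead of 2/12 (interval 2 to 48%), although the count for suspension under 10.5 would have been reached.

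**The case against.** The strongest reply is that the intent can be recovered. The threshold is *possibly* or above everywhere else, and a rule that skips the middle level has no rationale, so a sensible reader takes the two named levels as the ends of a range. That is probably what the authors meant. It does not settle the matter: section 10 itself writes out all three levels in 10.5, section 9 uses threshold wording where it means a threshold, and the definition of a primary endpoint should not rest on inferred intent.

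The second reply is that little depends on the wording. This is largely right. The 10.4 criterion rests on treatment-related toxicity without listing levels, no hypothesis test is planned on the safety endpoint, and 10.7.1 would describe the event among all treatment-related events. What is exposed is the primary rate and its interval.

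Third, 10.2.1.1 and 10.5 already differ in other ways: the exclusion of short infusion reactions, the end of the observation window, and who judges causality. So disagreement with 10.5 is weak evidence taken alone. The skipped level on the protocol's own scale carries the point.

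Fourth, the triggering event may be rare. Section 2.1 (Dose Rationale) reports no treatment-related adverse events under Version 2, and section 2.2.5 reports nothing above one Grade 2 event in the team's earlier intermittent vorinostat studies. The Version 2 experience was at a lower HXTC dose, so it limits the likelihood only in part. The 13-participant figures bring in a separate question about replaced participants and add little.

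**Conclusion.** The concern holds. As written, the primary safety endpoint leaves out one of the three positive causality levels on the protocol's own scale, without a stated reason and against the usage in section 9 and 10.5. It is most likely a slip.

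The consequence is confined to the reported primary rate and its interval. One affected participant would move the result from 1/12 to 0/12, and the upper 95% limit from 38% to 26%. That size assumes a Grade 3 or higher event rated exactly *probably*, no other qualifying event in that participant, and literal coding of the endpoint. The documents do not show how likely this is. The omission from the text is certain; any effect on the results is conditional. It should be corrected before analysis, so that which events count is not decided after the data are seen.

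**What to change.** In 10.2.1.1, have the endpoint count events *possibly, probably or definitely* related. If the sponsor does mean to leave out *probably*, say so there and give the reason, as the NOTE does for short infusion reactions.

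The cost is one inserted word. Causality is already recorded on five levels, so no new data are needed, and the sample size and the figures in 10.3 and 10.4 stand. The reported primary rate can only stay the same or rise.
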